## THE EFFECT OF PALM TOCOTRIENOL RICH FRACTION ON ALCOHOLIC FATTY LIVER DISEASE (AFLD): A PHASE II CLINICAL TRIAL

### ABSTRACT

**Background:** Alcohol abuse is a serious public health concern that is associated with many diseases, including alcoholic liver disease (ALD). The World Health Organization (WHO) reported that the use of alcohol has resulted in more than 3 million deaths every year and accounting for 5.9% of all deaths worldwide. As the metabolism of alcohol in individuals mainly depends on the liver, long-term and excessive alcohol consumption damages the liver leading to alcoholic fatty liver disease (AFLD). Since tocotrienols have been proven for their hepatoprotective effects in animal models of NAFLD, the aim of the study is to explore the potential role of tocotrienol rich fraction, in patients with AFLD.

**Methodology:** 26 patients with AFLD aged 18 to 65 years old, will be randomized into treatment (n=13) and placebo group (n=13). The treatment group will be prescribed with palm tocotrienol soft gel (200 mg twice daily) while the placebo group will receive refined, bleached, and deodorised (RBD) palm olein for six months. The subjects will be answering questionnaires related to alcohol consumption and their blood will be collected for the determination of liver function test, redox, haematological profile and inflammatory biomarkers. Fibroscan and FibroTest will be done twice during the 3-monthly follow-ups.

**Significance:** This study will validate the efficacy of tocotrienol in AFLD and its related morbidity, thereby producing data for subsequent phases of clinical trials. The findings of this study will also enhance the medicinal values of palm tocotrienol and diversify the usage of palm-based products in sustaining the Malaysian palm industry.

## **PROJECT SYNOPSIS**

Alcoholic misuse has resulted in 3.3 million deaths every year according to the World Health Organization (WHO) report on noncommunicable diseases [1]. Meanwhile, the National Health and Morbidity Survey (NHMS) 2019 data shows that the prevalence of current drinkers among Malaysian adults was 11.8%, of which 17.6% were risky drinkers [2]. Alcoholic liver disease has caused an estimated 48% of deaths from cirrhosis. The most common health problem associated with chronic alcoholism is alcoholic liver disease (ALD) [1]. Chronic alcohol abuse can result in a spectrum of liver injury that ranges from mild fatty infiltration to cirrhosis and hepatocellular carcinoma [3]. Fat accumulation in the liver cells is the earliest and most predictable response to alcoholic ingestion and is seen in 90% of heavy drinkers. The development of necroinflammation and fibrosis (alcoholic hepatitis or steatohepatitis) occurs in 10 to 35% of heavy drinkers [4]. It is important to recognize alcoholic hepatitis as patients with severe disease have extremely high short-term mortality rates, they can also develop portal hypertension in the absence of cirrhosis and the development of alcoholic hepatitis is a well-documented precursor for cirrhosis with long term risk 9 times higher than that for patients with fatty liver alone [1].

Pathogenesis of alcoholic hepatitis:

The liver is the main organ responsible for ethanol metabolism. Ethanol is metabolized by 3 major systems in the liver: alcohol dehydrogenase (ADH), cytochrome p450 2E1 (CYP2E1) and finally catalase. ADH and CYP2E1 convert ethanol to acetaldehyde which is then converted by aldehyde dehydrogenase (ALDH) to acetate. Acetaldehyde is a highly reactive and potentially toxic compound that is responsible for the many toxic effects of alcohol such as nausea, headaches and flushing.

Acetaldehyde is also postulated to play an etiologic role in alcoholic liver disease as it forms adducts with reactive residues on proteins or small molecules like cysteine [5]. These chemical modifications can alter or interfere with normal biological processes resulting in formation of substances such as acetaldehyde and malondialdehyde (MDA). The formation of MDA antigens during alcohol-induced liver disease likely contributed to the immunologic reaction associated with alcohol related liver damage [6]. Acetaldehyde has also been shown to impair mitochondrial glutathione transport and to sensitize hepatocytes to TNF-mediated killing. Lastly, acetaldehyde disrupts intestinal barrier function leading to endotoxemia and proinflammatory cytokine production.

Oxidative stress in the liver also increases after alcohol consumption. In hepatocytes, CYP2E1 activity increases after alcohol consumption [7]. The CYP2E1 system leaks electrons which initiate the oxidative stress [8]. Other sources of oxidative stress are infiltrating inflammatory cells in the liver. Oxidative stress in alcoholic liver disease is documented by detection of protein oxidation (eg: protein thiol or carbonyl products), lipid oxidation (eg: MDA), DNA oxidation (eg: oxodexyguanosine) or depletion of antioxidant defences (eg: vitamin E, glutathione, thioredoxin) [8]. Therefore, antioxidant supplementation could be a useful adjunct in the treatment of alcoholic hepatitis.

Diagnosis of alcoholic liver disease:

AFLD is currently defined by steatosis with a range of hepatic histopathologic changes including the presence of inflammatory infiltrates and varying degrees of fibrosis and cirrhosis that develop in the presence of chronic alcohol consumption, which is a known trigger factor that causes fat accumulation. Despite having comparable pathophysiological spectrum, the distinction between AFLD and NAFLD is determined by the amount of alcohol ingested, with AFLD being diagnosed based on the patient's history of regular alcohol usage, defined as >30 g/day in males and >20 g/day in females (according to clinical practice guidelines from the scientific associations for the study of liver diseases) [9, 10].

Apart from a reliable history of significant alcohol intake, no single laboratory or imaging testing can definitively confirm the diagnosis of ALD. Hence, its diagnosis is based on the compilation of clinical findings of hepatomegaly with signs of chronic liver disease, radiographic evidence of liver steatosis, fibrosis or cirrhosis, combined with abnormal biochemical results suggestive of liver injury [11].

Meanwhile, NAFLD is closely linked to obesity, caused by excessive food intake with a high-calorie, high-fat diet combined with a sedentary lifestyle [12, 13]. Most often, it is also associated with metabolic dysfunction [11, 14]. Obese people are more likely to develop

metabolic syndrome, and nonalcoholic fatty liver disease (NAFLD) has been identified as the hepatic manifestation of metabolic syndrome [15].

Therefore, in the context of this study, we propose to exclude the subjects who are obese (a body mass index (BMI) of 30 kg/ m^2 or higher) and with metabolic syndrome (based on the harmonised criteria) to minimise the risk of misclassification between AFLD and NAFLD.

Clinical evidence of decompensated liver disease such as ascites and its severity, hepatic encephalopathy; severity according to West Haven criteria, jaundice and coagulopathy must be assessed for. Evidence of alcoholic hepatitis as demonstrated by hepatocellular transaminitis of AST:ALT > 2:1 due to deficiency of pyridoxal 5'phosphate level in alcoholic patients, raised gamma glutamyl transpeptidase (GGT) raised mean corpuscular volume (MCV), raised total bilirubin with severely ill patients having coagulopathy as demonstrated by raised international normalised ratio (INR) and prothrombin time (PT). Patients with other forms of bleeding disorder, as well as those on anticoagulant or antiaggregant treatments are not eligible to participate in the trial. Patients who have been taking vitamin E, herbal supplements or other investigational products are also excluded.

Other types of liver disease, such as hepatitis B, hepatitis C and autoimmune hepatitis, hereditary hemochromatosis and non-alcoholic fatty liver disease will also need to be excluded. Assessment of the presence of advanced fibrosis or cirrhosis can be accessed via Fibroscan as well as FibroTest (FT) which is a serum marker used to calculate the degree of liver fibrosis. Patients should also be screened for hepatocellular carcinoma (HCC), a complication that can occur in alcoholic cirrhosis. Patients who are found to have HCC should be excluded from the study. Patients who have other coexisting chronic liver diseases (CLD) will not be eligible for recruitment as the presence of the CLD can confound the prognosis of alcoholic hepatitis. Once other chronic liver diseases have been ruled out, the severity of alcoholic liver disease will then be graded according to Maddrey's discriminant function.

The pathogenesis of ALFD involves oxidative stress and disruptions of lipid metabolism [7]. It also has been demonstrated that the response to hypoxia plays an essential role in the development of ALFD [8] and this in turn has been linked to mitochondrial radical oxygen species (ROS) generation. Currently, the most effective AFLD treatment is alcohol abstinence and there are still few effective pharmacological treatments for patients afflicted with this disease. Therefore, new therapies are urgently needed to prevent the progression of AFLD.

### **Background Information of the investigational product**

Vitamin E are well known for its potent antioxidant capabilities, while studies had also shown its positive effects on inflammation. Animal study had also shown the protective effect of palm tocotrienol on the liver [16]. The most common homologue of the vitamin E family investigated in treating liver disease is alpha tocopherol. Other homologues of vitamin E, namely tocotrienols, also exist in isomers designated as alpha, beta, gamma and delta, and they differentiate from analogous isomers of tocopherol by the presence of an unsaturated phytyl chain ('tail') as opposed to a saturated one in tocopherols [17]. Tocotrienols are preferentially distributed to the liver [18, 19] and alpha-tocotrienol has been reported to be 40-60 times more potent than alpha-tocopherol against lipid peroxidation in rat liver microsomes [20].

Several clinical studies have been conducted to evaluate the tocotrienol effects on the liver. All these studies have demonstrated the hepatoprotective effects of palm tocotrienols in their adult subjects. According to Patel et al. (2012) [29], tocotrienol attenuated the time-dependent rise in the Model for End Stage Liver Disease (MELD) score vs the alpha-tocopherol group in liver transplant subjects with end-stage liver disease. Magosso et al. (2013) [30] have demonstrated that in subjects with mild untreated hypercholesterolemia and ultrasound-proven non-alcoholic fatty liver (NAFLD), there is a normalization of the hepatic echogenic response in the tocotrienol-treated group vs. the placebo group.

There is also a significant reduction in aspartate aminotransferase (AST), alanine aminotransferase (ALT), malondialdehyde (MDA), and C-reactive protein (CRP) among subjects with ultrasound-proven non-alcoholic fatty liver (NAFLD) in the tocotrienol group vs. the placebo group, as reported by Pervez et al. (2018) [31]. These findings are in agreement with the outcomes of following study by Pervez et al. (2020) [21]. In their study subjects with NAFLD, tocotrienol significantly reduced AST, ALT, MDA, CRP, fatty liver index (FLI), and improved grading of hepatic steatosis on ultrasound, compared to the placebo group.

Tocotrienols are generally safe and are usually well tolerated. By participating in this research, it is possible that the treatment given to the subjects may or may not help improve their liver function. There is a risk that their condition will not get better and that the intervention won't work. The treatment given to them are usually in low doses and are unlikely to cause serious side-effects. However, in patients with bleeding disorders, tocotrienols might slow blood clotting. Tocotrienols may also interact with "blood thinners" such as warfarin and antiaggregants like aspirin, increasing the risk of bleeding. Thus, we advise against taking the treatment with these medications. Symptoms like nausea, diarrhea, stomach cramps, tiredness, dizziness, and blurred vision may rarely occur in cases of overdose. Allergic reactions to this supplement are rare; however, if they develop any symptoms of a serious allergic reaction, including rash, itching or swelling (especially of the face, tongue, or throat), dizziness, or trouble breathing, they should tell the doctor and get medical help right away. Venous blood taking would require a needle to pierce through their skin, which might also result in bruising and mild pain.

This trial will be conducted in compliance with the protocol, GCP and the applicable regulatory requirement(s). The population to be studied is adult patients aged 18-65 years, with a history of alcohol use disorder, who could comply with alcohol abstinence, and those with diagnosis of AFLD with lab evidence of Alcoholic Steatohepatitis (AST:ALT >2.0, elevated GGT) who come for follow up in Gastroenterology & Hepatology clinic in Hospital Canselor Tuanku Muhriz UKM (HCTM). Additionally, our research subjects were also recruited from the general public who responded to our recruitment poster on social media platforms.

### Research Gap

Concerns about the high prevalence of AFLD globally and the not fully understood reasons for its progression to more severe forms of liver diseases have led to the initiation of this interventional, double-blind placebo-controlled study. The aim of the investigation was to

evaluate the activity of tocotrienols in normalising hepatic echogenic response in adults with AFLD.

Currently, there are no effective treatment for alcoholic fatty liver disease apart from alcohol abstinence and making some lifestyle changes to control or reverse the fat build-up in the liver. An antioxidant and anti-inflammatory agent are speculated to enhance the healing of liver after alcohol abstinence, but this concept has not been effectively demonstrated in a clinical trial. Therefore, new therapies are urgently needed to prevent the progression of AFLD. Tocotrienol are well established for its potent antioxidant capabilities, while evidence had also shown its positive effects on inflammation. Thus, this study will validate the efficacy of tocotrienol in AFLD and its related morbidity, thereby producing data for subsequent phases of clinical trials. The findings of this study will also enhance the medicinal values of palm tocotrienol and diversify the usage of palm-based products in sustaining the Malaysian palm industry.

### **SCIENTIFIC IMPACT**

The health benefits of TRF in relation to liver health have been reported in vitro, in vivo and even human clinical studies. However, these clinical studies were conducted on subjects with liver cirrhosis and non-alcoholic fatty liver disease (NAFLD). To date, no data is available on human intervention studies involving TRF in alcoholic fatty liver disease (AFLD). It's important to carry out this clinical trial to find out if TRF would show the similar protective effect on subjects with AFLD, as it did with NAFLD.

In addition, the findings from this study could serve as the basis for future clinical studies related to liver diseases.

### **SOCIAL IMPACT**

This project outcome will give a significant impact to social and economy, locally and worldwide. Alcohol consumption is a major risk factor for chronic disease. Based on 58 studies from 17 Global Burden of Diseases (GBD) regions, alcohol use disorders accounted for 9.6% (7.7%-11.18%) of age-standardized disability-adjusted life years (DALYs) worldwide in 2010 [26]. Alcohol-induced liver cirrhosis was responsible for 0.9% of all global deaths and 47.9% of all liver cirrhosis deaths in 2010 [27].

Palm Oil is the largest agricultural contributor to Malaysia's gross domestic product (GDP) with a total of RM44.8 billion or 3.8 per cent of the GDP contribution in 2017 [28]. Malaysia is the largest tocotrienols manufacturer and the second largest palm oil producer in the world. The beneficial effect of Palm TRF in AFLD would encourage the local and global usage of Palm TRF and Palm Oil (the richest source of TRF) in pharmaceutical, dietary supplement, and functional food and drinks.

Meantime, there is no drug or treatment for AFLD at the moment. Palm TRF can be the potential adjuvant therapy to help the AFLD subjects in potentially maintaining healthy liver function. This project is also expected to produce a postgraduate student who will develop a strong background in clinical trial.

## **STUDY OBJECTIVES**

### **General:**

To determine the effects of palm tocotrienol rich fraction (TRF) on the progression of alcoholic fatty liver disease.

### **Specific:**

1. To determine the effects of TRF on fatty liver index and FibroScan score of patients with alcoholic fatty liver disease.
2. To determine the effects of TRF on the liver enzyme profile of patients with alcoholic fatty liver disease.
3. To determine the effects of TRF on metabolic status of patients with alcoholic fatty liver disease.
4. To determine the effect of TRF on inflammatory cytokines and redox status of patients with alcoholic fatty liver disease.

## **HYPOTHESIS**

1. TRF reduces fatty liver index and improves FibroScan score of patients with alcoholic fatty liver disease.
2. TRF normalises the liver enzyme profile of patients with alcoholic fatty liver disease.
3. TRF normalises the metabolic profile of the patients with alcoholic fatty liver disease.
4. TRF normalises the cytokines level and redox status of patients with alcoholic fatty liver disease.

## METHODOLOGY (STUDY DESIGN, WORK PLAN, MILESTONES)

This study would be a randomized, double-blind, placebo-controlled, phase 2 Study on the Effect of Palm Tocotrienol Rich Fraction on Alcoholic Fatty Liver Disease (AFLD). Patients who come for follow up in Gastroenterology & Hepatology clinic in PPUKM, with diagnosis of AFLD would be recruited in the study. Secondary data obtained from Casemix unit would also be screened to look for potential patients for the study.

### Primary Outcome Measures:

1. Change from baseline in Liver Enzyme Profile (Aspartate Aminotransferase [AST], Alanine Aminotransferase [ALT], and Gamma-Glutamyl Transferase [GGT]) at 3 and 6 months. Measured in units per liter (U/L) and reported as absolute and percentage change. Lower values indicate improved liver function.
2. Between-group difference in Liver Enzyme Profile (AST, ALT, GGT) at 3 and 6 months (Tocotrienol-Rich Fraction vs placebo). Measured in U/L. Lower values indicate improvement.
3. Change from baseline in Fatty Liver Index (FLI) at 3 and 6 months. Unitless score (range 0–100). Higher scores indicate greater hepatic steatosis (worse outcome). Reported as absolute and percentage change.
4. Between-group difference in Fatty Liver Index (FLI) at 3 and 6 months (Tocotrienol-Rich Fraction vs placebo). Range 0–100. Higher scores indicate worse steatosis.
5. Change from baseline in Liver Stiffness Measurement using Transient Elastography (FibroScan® score) at 3 and 6 months. Measured in kilopascals (kPa; typical range 2–75). Higher values indicate greater fibrosis. Reported as absolute and percentage change.
6. Between-group difference in Liver Stiffness Measurement (FibroScan® score) at 3 and 6 months (Tocotrienol-Rich Fraction vs placebo). Measured in kPa. Higher values indicate worse fibrosis.

\*Aspartate aminotransferase (AST) is usually used to detect liver damage. It is often ordered in conjunction with other liver enzymes, alanine aminotransferase (ALT) and gamma-glutamyl transpeptidase (GGT), or as part of a liver panel or comprehensive metabolic panel (CMP) to screen for and/or help diagnose liver disorders. The changes in these liver enzymes can also be used to monitor the compliance of patients toward alcohol abstinence.

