## SAMPLE SIZE CALCULATION

Sample size calculation was based on the comparison of two means derived from the effects of tocotrienol on fatty liver index (FLI) in patients with non-alcoholic fatty liver disease (NAFLD) (21). This is because the effectiveness of tocotrienol in alcoholic hepatitis has not been evaluated previously.

Formula of calculating sample size in clinical trial (22):

$$n = [(Z\alpha/2 + Z\beta)^2 \times \{2(\sigma)^2\}] / (\mu_1 - \mu_2)^2$$

Where:

$n$  = sample size required in each group

$\mu_1$  = mean of FLI for tocotrienol group = 12.82  $\mu_2$  = mean of FLI for placebo group = 3.86

$\sigma$  = standard deviation = 7.0

$Z\alpha$ : This depends on level of significance, for 5% this is 1.96  $Z\beta$ : This depends on power, for 80% this is 0.84

$$n = [(1.96 + 0.84)^2 \times \{2(7.0)^2\}] / (12.82 - 3.86)^2$$

The sample size calculated is 10 per group. Taking into account 20% of subjects might be lost to follow up, the number of each group is adjusted to 13. Hence, the total sample size required for this study is 26 individuals.

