### **STATISTICAL ANALYSIS**

Normality of the data will be assessed through Shapiro-Wilk test. Since the study adopts a time x group design, mixed-design ANOVA will be used to compare the effects across time (within group) and between treatment groups. Small effect analysis will be used as the pairwise post hoc analysis. If the data is skewed, the data will be analysed with Kruskal Wallis test and Mann Whitney U-test with Bonferroni correction for type-1 error. All analyses will be performed using Statistical Package for Social Sciences version 23 (IBM, Armonk, USA). The data will be presented as mean (standard deviation). A p-value less than 0.05 is considered statistical significance.

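### Five unranked primary measures at two visits, with no success rule and only FLI sized: the between-arm familywise error is uncontrolled, and within-arm primaries could be met without a drug effect

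*Protocol*

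**What the plan says.** Protocol, Primary Outcome Measures, has six numbered entries on five measures. Entries 1, 3 and 5 are changes: "Change from baseline in Liver Enzyme Profile (Aspartate Aminotransferase [AST], Alanine Aminotransferase [ALT], and Gamma-Glutamyl Transferase [GGT]) at 3 and 6 months"; "Change from baseline in Fatty Liver Index (FLI) at 3 and 6 months"; and "Change from baseline in Liver Stiffness Measurement using Transient Elastography", also at 3 and 6 months. Entries 2, 4 and 6 set the arms against each other on the same measures, for example "Between-group difference in Liver Enzyme Profile (AST, ALT, GGT) at 3 and 6 months" and "Between-group difference in Fatty Liver Index (FLI) at 3 and 6 months". The change entries carry a reporting instruction, as for the enzymes: "Measured in units per liter (U/L) and reported as absolute and percentage change". The between-group entries are in native units only. No measure or visit is singled out, and there is no order and no success rule.

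Protocol, Statistical Analysis, plans a mixed-design ANOVA of time by group with pairwise post hoc comparisons, and states "A p-value less than 0.05 is considered statistical significance". Bonferroni is mentioned only for the rank tests used when data are skewed, and the set of tests it would cover is not given.

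Protocol, Sample Size Calculation, rests on the "effects of tocotrienol on fatty liver index (FLI) in patients with non-alcoholic fatty liver disease", with 5% two-sided (1.96) and 80% power (0.84). It does not name the visit, or say whether the two means are levels or changes.

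Protocol, Randomisation and Treatment, justifies six months of treatment by saying that the mild disease recruited is expected to resolve with abstinence alone. The note to the exclusion criteria requires abstinence of every patient.

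**The concern.** If several primary results are each judged at 5% and nothing says which one decides, any one of them can be presented as the trial's success. The 5% in the sample size calculation then no longer describes the risk of a wrong primary conclusion. The abstract says the trial will validate efficacy and feed later phases, so a chance finding on one enzyme at one visit could carry forward.

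The change-from-baseline entries are a second route to a false claim. They are listed as primaries in their own right, separate from the between-group entries, and the ANOVA is described as comparing effects over time within group. In a population expected to improve through abstinence, a significant change within the tocotrienol arm says nothing about tocotrienol.

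**Working it through.** **1. The plan's own figure.** Inputs from Sample Size Calculation: means 12.82 and 3.86 (difference 8.96), SD 7.0, z-values 1.96 and 0.84.

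n = (1.96 + 0.84)² × 2 × 7.0² / 8.96² = 7.84 × 98 / 80.28 = 9.57, so 10 per group. With 20% loss, 10 / 0.8 = 12.5, so 13 per group and 26 in total. The arithmetic reproduces, for one FLI comparison at an undivided 5%.

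**2. Number of between-arm tests.** The text allows two counts:
- Five: one time-by-group test per measure, with both visits inside the model.
- Ten: 5 measures × 2 visits, as entries 2, 4 and 6 are listed.

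Percentage change is not counted, because it is only to be reported.

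**3. Familywise error between arms.** If tests are independent, it is 1 − 0.95^k:
- k = 5: 1 − 0.95⁵ = 22.6%
- k = 10: 1 − 0.95¹⁰ = 40.1%

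The measures will be correlated, and the protocol gives no correlations, so a range is assumed. Simulation used 10 per arm and no true effect. The five-test column uses the time-by-group test with three visits and an assumed between-visit correlation of 0.6. The ten-test column uses equally correlated two-sample t-tests.

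| Assumed correlation | Five tests | Ten tests |
|---|---|---|
| 0 | 23% | 40% |
| 0.3 | 21–22% | 36% |
| 0.5 | 19% | 29–30% |
| 0.7 | 15–16% | 22% |

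Every cell is at least three times the nominal 5%.

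**4. Change-from-baseline entries.** Simulation of ten within-arm tests (5 measures × 2 visits, absolute scale) in the tocotrienol arm only. Assumptions not in the documents: 10 patients, log-normal data with coefficient of variation about 0.3, between-visit correlation 0.6, between-measure correlation 0 to 0.7.
- No change over time: at least one p < 0.05 in 26–37% of trials.
- A 0.5 SD improvement in both arms from abstinence (1 − exp(−0.5 × 0.3) = 14%) and no drug effect: 79–97%.

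The 0.5 SD is illustrative; the protocol states the expectation of improvement but not its size.

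**5. Cost of keeping every measure primary.** FLI power by t-test with d = 8.96 / 7.0 = 1.28 and 10 per arm:
- 5%: 77%
- 1% (Bonferroni for five): 51%
- 0.5% (Bonferroni for ten): 40%

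The protocol's normal approximation gives 82%, 61% and 52%. By its formula, 80% power for FLI would need:
- five tests: (2.576 + 0.842)² × 98 / 80.28 = 14.3, so 15 evaluable and 15 / 0.8 = 18.75, so 19 randomised per arm
- ten tests: (2.807 + 0.842)² × 98 / 80.28 = 16.3, so 17 evaluable and 17 / 0.8 = 21.25, so 22 randomised per arm

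AST, ALT, GGT and stiffness cannot be sized, because no effect or SD is given for them.

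**The case against.** The strongest reply is that the stated analysis is a time-by-group ANOVA, with visit comparisons only post hoc, so there are five primary tests and not ten. That reading is fair, and the five-test figures are shown for it. It does not settle the matter. The protocol does not make the post hoc tests conditional on the overall term, the outcome list names both visits, and five tests still give 15–23%.

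Three stronger readings are tempting and are not supported:
- **A false positive is likely.** Between arms the risk stays at or below 40% in every case examined. It passes one half only if within-arm change can count as success and patients in both arms improve, which rests on an assumed size of improvement.
- **Two scales double the tests.** Percentage change is attached only to entries 1, 3 and 5, and the word used is reported, not tested.
- **Everything is unadjusted.** Bonferroni is stated for skewed data. What is missing is a defined family and any extension to the ANOVA branch or across the five measures.

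It can also be said that this is a 26-patient phase II trial meant to inform later phases, and that an unseen statistical analysis plan might hold a hierarchy. The small scale tempers what is at stake. A later plan could add a procedure, but the primary list, the threshold and the sizing are fixed in the protocol, so it would have to override them.

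Finally, objective 1 pairs FLI with FibroScan, so demoting stiffness is a scientific choice. That stands, and is counted as a cost below.

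**Conclusion.** The point holds. The protocol names five unranked primary measures at two visits, gives no success rule, uses a general 5% threshold and sizes only FLI. As written, the between-arm familywise error is about 15–23% on the five-test reading and 22–40% on the ten-test reading. Those ranges rest on assumed correlations from 0.7 down to 0 and 10 evaluable patients per arm.

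The within-arm primaries add a separate risk, which follows from the protocol's own expectation of recovery with abstinence. Its direction is clear, but its size (79–97% in the illustration) depends on the assumed improvement. The sample size arithmetic itself is correct; the defect is that it covers one of five primary measures at an alpha not shared with the others.

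**What to change.** Name one primary: the between-arm difference in absolute change in FLI from baseline to one stated visit, two-sided 5%. FLI is the only endpoint sized. Month 6, the end of treatment, is the natural visit, but this is a choice: the sample size section does not fix it.

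Make AST, ALT, GGT, liver stiffness and the other visit secondary, either tested in a fixed order after the primary or reported with 95% confidence intervals and no confirmatory claim. Report within-arm changes and percentage change descriptively only. Apply the same primary and the same error rule whether the data are normal or skewed.

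Cost: the enzymes and stiffness lose primary status, and the protocol and any registry wording must be changed. Some sections describe recruitment and assignment in the past tense; if enrolment has begun, the change needs a dated, justified amendment before unblinding. No extra patients or visits are needed, and 10 evaluable and 13 randomised per group stand as calculated. If the sponsor prefers to keep several primaries, it must define the family, split alpha and resize, to about 19 randomised per arm for five tests at the FLI effect, and supply effects and SDs for the other four measures.
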